Training of the lateral pterygoid muscle in the treatment of anterior temporomandibular joint disc displacement with reduction with pain

Physical exercises for temporomandibular disorders

Unique Protocol ID: 0016032021

Document Date: March 16, 2021

List of abbreviations

| Diagnostic Criteria for Temporomandibular Disorder |
|--|
| Disc displacement with reduction |
| Jaw Functional Limitation Scale |
| Millimeter |
| Numeric rating scale |
| Temporomandibular Disorder |
| Temporomandibular Joint |
| |

Abstract

Temporomandibular Disorders are a common clinical picture that appear in particular in people between the age of 20 and 40 years. About 33% of the total population shows symptoms and signs of TMD. Among the temporomandibular joint disorders anterior disc displacement appear to be the most common. In case of limitations of jaw movements and or pain conservative methods including combinations of behavior change, physiotherapy, stabilization appliance therapy and medication are most popular. The benefit of a self-treatment program to strengthen the lateral pterygoid muscle and to learn a properly executed lower jaw sideways movement to achieve pain reduction is up to now not well investigated. The aim of this study is to examine the effectiveness of muscle training for the treatment of patients with anterior disc displacement with reduction (DDWR). 60 patients with DDWR and pain (≥18 years) will be randomly allocated to two groups: 1. Physical exercises, 2. Stabilization appliance therapy. All patients receive a functional examination according to the Diagnostic Criteria for Temporomandibular Disorders (DC/TMD) at baseline.

The training in group 1 includes eccentric and concentric counter-movements of the lower jaw muscle to strengthen and restore a physiological lateral movement of the mandible. The muscle exercises should be performed once a day with 5-6 repetitions per side. The treatment with an equilibration appliance in the lower jaw serves as a comparison group. Patients are instructed to wear the appliance while sleeping. The wearing rhythm is described as intermittent. (three nights - wearing the appliance, one night – not wearing the appliance). The primary target variable is the occurrence of pain in the head and joint area before and during therapy. The variable is measured using a numeric rating scale (NRS; 0-10) during the baseline examination and control check-ups after 2, 4 and 6 months.

Scientific background

The literature describes the cause of a temporomandibular disorder (TMD) as a multifactorial event [20]. It can be influenced by anatomical, neuromuscular, traumatic or psychosocial factors [3]. Disturbances often occur in the condyle-disc complex of the temporomandibular joint [4]. The relationship between the articular disc and the condyle head is pathologically altered. The Diagnostic Criteria for Temporomandibular disorders (DC / TMD) describe the displacement of the disc in 4 different forms: disc displacement with reduction; disc displacement with reduction and intermittent locking; disc displacement without reduction with limited opening and disc displacement without reduction without limited opening [17]. TMDs are a common clinical picture that appears in particular in people between the age of 20 and 40 years. About 33% of the total population show signs and symptoms of TMD [16], [21].

Studies prove that the displacement of the disc with reduction is the most common disorder among temporomandibular joint disorders [6], [19]. According to the DC / TMD, this clinical picture shows intracapsular and biomechanical alterations. If the mouth is closed, the articular disc is often located in front of the mandibular condyle; if the mouth is opened, the disc moves back to its original position on the condyle. Anterior disc displacement appears to be the most common, although a medial or lateral displacement is also possible. During the disc repositioning clicking, popping or snapping noises are usually recorded [17]. Temporomandibular joint disorders such as disc displacement, can also cause pain [7], [8]. Overstretching of the posterior ligament and a compression of the bilaminar zone mandibular movements can be pain-related. Therefore, clicking, popping or snapping noises in the area of the temporomandibular joint (TMJ) correlate with pain in the surrounding tissue. Those complaints intensify when opening the mouth or chewing food [2], [15].

The treatment of TMD should be oriented on evidence-based procedures that are easy to implement in practice and have a long-term positive effect on the patient's symptoms [22]. Conservative methods including combinations of behavior change. physiotherapy, splint-therapy and medication are most popular [10], [13], [14]. The physiotherapeutic treatment should pursue different strategies, including manual therapy methods (e.g. mobilization and stretching of the temporomandibular joint and / or the neck area) and the demonstration of exercises in everyday life (e.g. selfmobilization and stretching of the masticatory muscles and / or cervical spine) and in addition educating the patient (e.g. about the perception of parafunctions or relaxation techniques) [11], [22]. Conservative attempts for patients with TMD should be the first choice. However, there is still no clear data situation and the data pool of randomized clinical studies on this topic needs to be improved. So far studies demonstrate a positive effect of the tested therapy forms. But the individual studies differ greatly in terms of the patient pool, diagnosis, treatment modalities and the result [18]. Furthermore, a precisely described procedure is missing in some papers. Therefore, an exact reproducibility for practitioners is not executable. More research is needed into the benefits of various non-invasive treatments for TMD.

The primary goal of this study is to decrease the ambiguity in this scientific field. In the past various manual and physiotherapeutic exercise methods have already been tested [9], [12].

This study is also intended to examine the effectiveness of muscle training for the treatment of patients with anterior disc displacement with reduction. The exercises are primarily supposed to train the lateral pterygoid muscle. The treatment with an stabilization appliance in the lower jaw serves as a comparison group.

Hypothesis

In this study, patients with anterior disc displacement with reduction are treated with muscle training of the lateral pterygoid muscle. The treatment with an stabilization appliance in the lower jaw serves as a comparison group.

1. By strengthening the lateral pterygoid muscle and learning a properly executed lower jaw sideways movement, pain reduction is achieved in patients with an anterior disc displacement with reduction.

2. By strengthening the lateral pterygoid muscle and learning a properly executed lower jaw sideways movement, the cracking phenomenon during jaw opening or jaw closing movements in patients with an anterior disc displacement with reduction is reduced.

Study design

Prospective, randomized study with control group, stratified by gender.

The type of therapy is assigned randomly.

The study is unblinded for the doctor and patient.

It is not possible to blind the practitioner because he is familiar with the forms of treatment. Since the practitioner and examiner are one and the same person in the practice, blinding is not possible here either.

It is also not possible to blind the patient, as they are able to research the form of therapy. During the last examination, the participants of the study are asked whether they have researched the respective form of treatment.

Target criteria

Primary outcome variable

The primary outcome variable is defined as the change of orofacial pain in the head and joint area after initiating the therapy measured by numeric rating scale (NRS; 0-10, 0: no pain, 10: worst imaginable pain) at the time of the follow-up appointments.

Secondary outcome variables

The following parameters are recorded as secondary target variables:

- Change in number of clicking noises in the TMJ during jaw opening or jaw closing movements
- Change in force degrees for lateral movement of the mandible according to Janda (modified scale from 4- to 5)

- Change in interincisal distance during maximum unassisted opening (in mm)

Sample size estimation

Determine the required sample size based on the numerical pain scale 0-10 for the primary target variable. Norms are pain scores of 3-5 (myofascial pain) in patients with craniomandibular dysfunction (CMD). To determine a mean difference of 2 level (standard deviation of 2 between the two treatment groups, they must each comprise 24 patients.

Test method: Wilcoxon-Mann-Whitney test with a two-sided α = 0.05, a power = 0.90 assuming the family of logistic distributions (G * Power, version 3.1.) The net sample consists of 48 persons. Assuming a drop out 6 patients per group, a total sample of 60 persons must be calculated.

Methods of data collection

The data is collected electronically and saved in the patient file. The required values for each patient were taken from the computer system of Dr. med. dent. [name]'s dental practice.

The patient fills in a symptom-related questionnaire before the initial examination starts. The questionnaire is based on the current requirements of the DC / TMD. Demographic data as well as questions about general pain, headaches, jaw noises or locking are answered. In addition, each patient completes a questionnaire on the grading of chronic pain (Version 2.0), the Jaw Functional Limitation Scale (JFLS-8) and the Oral Behavior Checklist.

A functional examination is created during the baseline check-up. It is used to capture masticatory muscle and temporomandibular joint complaints based on a detailed anamnesis and subsequent clinical examination via palpation and inspection of the orofacial area. A standardized examination procedure adapted to the DC / TMD is used for this procedure.

During the screening examinations (after 2, 4 and 6 months), the functional status as well as the primary (pain when opening or closing the mouth) and secondary (occurrence of the cracking phenomenon when opening or closing the mouth, Janda degrees of strength for laterotrusion movement, interincisal opening) target variables will be collected.

Patient characteristics

Treatment groups

Treatment group 1: patients with anterior disc displacement with reduction **Therapy:** Static stretching and isometric contraction exercises of the lateral pterygoid muscle are used to strengthen and restore a physiological lateral movement of the mandible. The training is supervised in the dental practice and continued with selfexercises at home. The therapy is accompanied by an exercise movie on DVD produced by Dr.med.dent [name].

Treatment group 2: patients with anterior disc displacement with reduction. **Therapy:** Stabilization appliance for the lower jaw

Group size: 30 patients per group (60 patients in total)

Description of the recruitment: The patients will be recruited in the dental practice

Inclusion Criteria

- Orofacial pain in the joint or muscles, degree NRS≥3
- Clicking phenomenon during TMJ opening or closing movement
- Deviation movement during opening of the lower jaw
- Age: \geq 18 years
- Legal competence and presence of the signed declaration of consent

Exclusion Criteria

- Age <18 years
- Drug abuse
- Depression
- Polyarthritis

Test procedure

Examiners

All examinations and determinations of the individual measurement data are carried out by Dr. med. dent. [name], in his dental practice in Steina. The exercise instructions are supervised by [name] in the dental practice in Steina.

Baseline examination

For the baseline examination the patient's anamnesis is recorded and the dental status is ascertained.

A panoramic radiograph must be available prior to the treatment in order to assess dental health and ensure the success of the treatment and it must not be older than 6 months. Such an X-ray can be realized by the volunteer's general dentist or the specialized dental practice in Steina.

The functional examination is based on the standardized DC / TMD.

Also, the inclusion and exclusion criteria for the planned form of therapy are checked. The assessment of the degrees of strength according to Janda during the lateral movement of the mandible requires a pain-free and coordinated sequence of movements. Subjects who experience unilateral or bilateral pain during this lower jaw movement cannot be included in the study.

The assessment of patients, who are assigned to the muscle training group and who are diagnosed with a pain-free, but uncoordinated movement pattern, is based on the

Groot Landeweer coordination scale (I-III). The subjects who only achieve Grade II or III must first perform exercises to improve coordination during laterotrusion (exercises with a spatula). The development of the coordinative ability is reassessed through weekly checks. By achieving level I (according to Groot Landeweer), the strength level (according to Janda) for the lateral movement of the lower jaw can be determined. Instructions in muscle training can be given.

These examination procedures are part of the routine examination in the "TMD Competence Center Westlausitz" for patients with temporomandibular disorders.

Coordination according to Groot Landeweer [1]:

I Coordinated execution of the movement
II Execution of the movement only by using facial muscles and / or masticatory muscles
III Inability to perform the movement

Modified scale of the degrees of force according to Janda for laterotrusion [5]:

| 4- | Full movement against a slight resistance |
|----|--|
| 4 | Full movement against moderate resistance |
| 5- | Full movement against clear resistance |
| 5 | Full movement against strong resistance / maximum strength |

Randomization

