The stabilization appliance is incorporated by the dentist and the static and dynamic occlusion is checked. A tension-free fit of the appliance on the lower jaw is necessary. Additionally, equal contacts in the side teeth area and incisors guidance in the case of mandibular protrusion are checked visually and by using occlusion foil. During mandibular lateral movement only the canine guidance takes place and is also registered optically and by using occlusion foil. Interference contacts should be adjusted.

The patient is instructed to wear the stabilization appliance while sleeping. The wearing rhythm is described as intermittent. (three nights - wearing the appliance, one night – not wearing the appliance).

Control appointment for stabilization appliance group (1 week after integration)

The first inspection takes place one week after the integration. The surface contacts in the side teeth area as well as the incisor and canine guidance are checked again.

First control appointment (2 months after start of therapy)

Two months after starting the therapy, an examination is carried out with a renewed assessment of the functional status. The primary (pain when opening or closing movements of the mouth) and secondary (occurrence of the cracking phenomenon when opening or closing movements, Janda degrees of strength in lateral movement of the mandible, interincisal opening distance) target variables are recorded.

Second control appointment (4 months after start of therapy)

A second check is carried out 4 months after starting the therapy. The functional findings as well as the primary (pain when opening or closing the mouth movement) and secondary (occurrence of the cracking phenomenon when opening or closing the mouth movement, Janda strength levels for lateral movement of the mandible, interincisal opening distance) target variables are recorded.

Third control appointment (6 months after the start of therapy)

The last examination takes place 6 months after starting the therapy. The functional status as well as the primary (pain when opening or closing the mouth movement) and secondary (occurrence of the cracking phenomenon when opening or closing the mouth movement, Janda strength levels for lateral movement of the mandible, interincisal opening distance) target variables are recorded.

Patient Safety

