In addition, the study groups are differentiated according to the categorical factor of gender.

Statistical analysis

The evaluation of the target variables is carried out using descriptive and inductive statistics.

In the descriptive statistical representation, the usual characteristic values such as frequency, mean values, standard deviation and range of values (minima, maxima) are used.

Possible differences in the study groups are analyzed using parametric (double t-test) and non-parametric (Mann-Whitney U-test) methods. The Chi²- test is used to analyze possible relationships between the nominally scaled values (e.g. gender). The interpretation is based on a 95% confidence interval. The hypothesis testing procedure is based on an error probability of 5% [p = 0.05], which is often used in studies.

The evaluation of the blinded data is carried out by [name].

Data management

Data collection

The data for each patient are taken from the electronic patient file of Dr. med. dent. [name] in Steina. This includes the questionnaire consisting of the baseline exmaination, x-rays, functional status, as well as the primary (pain when opening or closing the mouth) and secondary (occurrence of the cracking phenomenon when opening or closing the mouth, Janda degrees of strength in laterostrusion movement, interincisal opening distance) target variables.

The forms are filled out, dated and signed by the test subjects or persons who are authorized to document them (dental practice employees).

Data processing

The data entry in the electronic patient file is carried out by the examiner Dr.med.dent. [name] or his employees. All questionnaires and findings sheets that have been filled out by hand are scanned and also saved in the electronic file of each volunteer.

The use of the data takes place in accordance with legal regulations and requires a voluntarily submitted and signed declaration of consent by the test persons before participating in the clinical study.

The collected data may be passed on to [name] and the study director in pseudo-anonymized form for the purpose of scientific evaluation.

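### The unblinded treating dentist is also the examiner for the primary pain score; the plan does not say how the score is obtained and describes no patient-completed form at follow-up

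*Combined protocol and SAP*

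**What the plan says.** On blinding, Study design states: "The study is unblinded for the doctor and patient". For the examiner it adds: "Since the practitioner and examiner are one and the same person in the practice, blinding is not possible here either".

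On who measures, the Examiners section reads "All examinations and determinations of the individual measurement data are carried out by" the dentist, in his own practice. Methods of data collection and the three control-appointment sections list the primary pain variable among the items collected at the 2-, 4- and 6-month examinations.

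On how pain is measured, the primary outcome is "measured by numeric rating scale (NRS; 0-10, 0: no pain, 10: worst imaginable pain) at the time of the follow-up appointments". This gives the instrument and the time. It does not say who asks, who writes the score down, or whether that happens before or during the consultation.

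On self-completion, Methods of data collection says of baseline: "The patient fills in a symptom-related questionnaire before the initial examination starts". The Data collection section says "The forms are filled out, dated and signed by the test subjects or persons who are authorized to document them", meaning practice employees, without assigning items to one or the other. Nothing comparable to the baseline questionnaire is described for follow-up.

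The only step described as blinded is the evaluation of the data, in the Statistical analysis section.

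**The concern.** The primary comparison rests on one subjective 0-10 score. The person responsible for measuring it knows each patient's arm, fits and adjusts the appliance in one arm, and works at the centre that developed the exercise film used in the other. If the score is taken in conversation, the patient may answer to please, and the examiner may probe or round differently by arm. Either would enter the treatment difference directly.

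The plan treats the missing blinding as a consequence of one person holding both roles. That is a staffing arrangement, and the argument matters less for pain than for the clinical measurements: a patient's own rating needs no examiner to record it. The plan already relies on patient-completed forms at baseline, but describes none at the visits where the treatment effect is measured.

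**Working it through.** The core of this point is a reading of the text, so the relevant sections are set side by side first. The arithmetic then checks whether any design figure is affected and shows what an assumed bias would do.

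1. **Who records.** Study design: practitioner and examiner are the same person, unblinded. Examiners: that dentist makes all determinations of measurement data. Methods of data collection and the control appointments: the primary pain variable is among the items collected at those examinations. Together these place the primary outcome within the unblinded dentist's examination.

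2. **How it is recorded.** The primary outcome definition gives no mode of administration. Data collection allows forms to be completed by patients or employees. Data processing has the examiner or his employees enter the data. The mode is therefore open, and nothing in the text keeps the dentist out of it.

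3. **What the blinded evaluation can do.** It prevents the analyst's knowledge of the arm from influencing the analysis. A score shifted at collection is already in the data set by then.

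4. **Which pain.** The Abstract and the primary outcome definition refer to pain in the head and joint. Methods of data collection, the control appointments and the Data collection section refer to pain on jaw opening or closing. A sheet completed before the consultation suits recalled pain but may not capture pain provoked during the examination. The definition has to be settled before the form is written.

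5. **Design figures.** Inputs from Sample size estimation: difference 2, SD 2, two-sided α 0.05, power 0.90, Wilcoxon-Mann-Whitney test with a logistic distribution. Noether's formula with equal groups is N = (1.960 + 1.282)² / [12 × 0.25 × (p − 0.5)²]. For a logistic shift of one SD, p = 0.773, so N = 10.51 / (3 × 0.273²) = 47.0, which rounds up to 24 per group. Dropout is 6/30 = 20%, and 48/(1 − 0.20) = 60. The plan's 24, 48 and 60 are reproduced (other standard methods give 21 to 26 per group). Who records the NRS does not enter the formula, so these figures stand.

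6. **Illustration only.** The documents give no size or direction for a recording bias, so the values of b below are assumptions. Take SD 2, a two-sided t-test at 5%, and a difference b between arms caused by recording alone. The noncentrality is (b/2) × √(n/2) with 2n − 2 degrees of freedom. With no true difference:

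| Assumed b (NRS points) | Noncentrality, n = 24 | False-positive rate, n = 24 | False-positive rate, n = 30 |
|---|---|---|---|
| 0 | 0 | 5% | 5% |
| 0.25 | 0.125 × 3.464 = 0.43 | 7% | 8% |
| 0.5 | 0.25 × 3.464 = 0.87 | 14% | 16% |
| 1.0 | 0.5 × 3.464 = 1.73 | 40% | 48% |

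Bias can also work against a true effect. If the planned 2-point difference were shrunk by 0.5 to 1.5 points, t-test power at 24 per group would fall from 92% to 72%.

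**The case against.** The strongest reply is that the NRS is a patient rating, that no sentence says the dentist asks for it aloud, and that the rule on forms permits patients to complete them at any visit. This stands in part. A reader might infer that the dentist personally takes the score; the documents make that the natural reading but do not state it. If self-completion is already intended, one sentence in the plan settles the matter.

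A reader might also infer that the dentist delivers both therapies. The text does not establish this. The dentist fits the appliance ("The stabilization appliance is incorporated by the dentist and the static and dynamic occlusion is checked"), but for the other arm "The exercise instructions are supervised by" is followed by a removed name, which may or may not be the same person. The point does not depend on it: the unblinded dentist treats at least the appliance arm and examines both.

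Nor can it be said that the plan takes no protective step. It discloses the lack of blinding, uses a standardised DC/TMD-based examination, asks patients at the last visit whether they researched their therapy, and has blinded data evaluated. None of these acts where the pain score is obtained.

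Finally, a self-completed sheet cannot deliver blinding. Patients know their treatment, and the sheet goes to the same practice, so expectation and the wish to please remain. That is correct, and it limits the gain.

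**Conclusion.** The point holds as a cheap improvement. Followed as written, the plan leaves the primary outcome open to influence from an unblinded examiner at collection, does not state how the NRS is obtained, and does not carry its own baseline practice of patient-completed forms over to follow-up. The blinded evaluation does not address this.

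The size of any bias cannot be calculated from the documents. The rates in the illustration depend on assumed biases of 0.25 to 1.0 points, an SD of 2 for the analysed score and a t-test. They show sensitivity and are not evidence that bias of that size, or in a given direction, will occur. No sample-size figure changes. A reader might infer that self-completion would make the pain comparison free of bias; it would only reduce the examiner's direct influence on the recorded score.

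**What to change.** - Reconcile the definition of the primary variable (head and joint pain, or pain on jaw opening or closing), and print that one definition on the form.
- At baseline and at 2, 4 and 6 months, have the patient mark the 0-10 NRS on a dated, signed sheet before seeing the dentist. Baseline is included because the outcome is a change, and both scores should be obtained in the same way.
- Have existing practice employees scan the sheet into the patient file. State that the dentist does not re-ask or alter the score.
- Report clicking, Janda grade and opening distance as assessed unblinded. This describes how they were obtained; it does not withdraw the second hypothesis, on joint noises.
- Acknowledge in the protocol and the report that expectation bias in unblinded patients remains.

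The cost is one sheet and a few minutes per visit. Employees already complete forms, and handwritten forms are already scanned, so no additional assessor is needed. Sample size, treatment and visit schedule are unchanged.

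### Does 24 patients per group contradict the stated 90% power under the logistic assumption?

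*Combined protocol and SAP*

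**What the plan says.** The Sample size estimation section of the protocol sizes the trial on the primary pain outcome: "Determine the required sample size based on the numerical pain scale 0-10 for the primary target variable". The effect and the result come together: "To determine a mean difference of 2 level (standard deviation of 2 between the two treatment groups, they must each comprise 24 patients". The test, error rates and parent distribution follow: "Wilcoxon-Mann-Whitney test with a two-sided α = 0.05, a power = 0.90 assuming the family of logistic distributions", with the software named as G*Power, version 3.1. The section then states that "The net sample consists of 48 persons" and closes with the allowance for losses: "Assuming a drop out 6 patients per group, a total sample of 60 persons must be calculated". The Treatment groups section and the SAP's Number of cases section repeat 30 per group and 60 in total. The Randomization section gives 1:1 allocation. The formula or program option that turned these inputs into 24 is not stated.

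**The concern.** A reader who enters these inputs into a standard Wilcoxon-Mann-Whitney calculation may well get a different answer. The rank test is more efficient than the t-test when the parent is logistic, and the A.R.E. method with that parent asks for 21 per group, not 24. The same method with a normal parent asks for exactly 24. The obvious suspicion is that the calculation used a normal parent and was labelled logistic.

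If so, the power statement would rest on a basis other than the one reported, and the margin above 90% would be smaller than the logistic label implies. At the least, the figure would not be reproducible from the plan.

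**Working it through.** **Inputs.** From Sample size estimation: difference 2 and SD 2, so d = 2/2 = 1; two-sided alpha 0.05 (z = 1.960); power 0.90 (z = 1.282); logistic parent. From Randomization: 1:1 allocation.

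**Step 1: reproduce the plan's figure.** Noether's formula for the total sample is N = (z_alpha + z_beta)² / [3(p − 0.5)²], where p is the probability that a patient in one group scores above a patient in the other.

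- A logistic distribution with SD 2 has scale 2√3/π = 1.103, so the shift in scale units is δ = 2/1.103 = 1.814.
- p = e^δ(e^δ − 1 − δ)/(e^δ − 1)² = 6.1337 × 3.3199 / 5.1337² = 0.7727.
- N = (1.960 + 1.282)² / (3 × 0.2727²) = 10.51/0.2230 = 47.1, or 23.56 per group, rounded up to 24.
- Power at N = 48: √(3 × 48 × 0.2727²) − 1.960 = 3.272 − 1.960 = 1.312, which corresponds to 0.905.

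This uses the stated test, parent, alpha, sidedness, effect and power, and it returns the stated 24.

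**Step 2: compare other methods.** The A.R.E. method uses a noncentral t with noncentrality d√(nA/2) and 2nA − 2 degrees of freedom, where A = π²/9 = 1.097 for a logistic parent and 3/π = 0.955 for a normal one. At n = 24 the logistic noncentrality is √(24 × 1.097/2) = 3.628; the normal one is √(24 × 0.955/2) = 3.385.

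| Method | Parent | Power at 24 per group | Smallest n per group for 90% |
|---|---|---|---|
| Noether | logistic | 0.905 | 24 |
| Simulated Mann-Whitney | logistic | 0.933 | 22 |
| Lehmann large-sample | logistic | 0.941–0.943 | 21 |
| A.R.E. | logistic | 0.945 | 21 |
| A.R.E. | normal | 0.912 | 24 |
| Simulated Mann-Whitney | normal | 0.909 | 24 (about 0.90 at 23) |
| Noether | normal | 0.878 | 26 |

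**Step 3: why the logistic rows differ.** Noether's formula applies the null variance of the rank statistic under the alternative as well. With p at 0.77 the true variance is smaller, so the formula understates power, here by 0.933 − 0.905 = 2.8 points. That is a known property of a recognised approximation, and it errs on the safe side.

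**Step 4: losses.** 24 + 6 = 30 per group; 6/30 = 20%, and 24/(1 − 0.20) = 30. Twice 30 is 60, as stated throughout.

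**The case for a change.** The strongest case for a correction is that two different bases both give 24: Noether with a logistic parent, and A.R.E. with a normal parent. They rest on different assumptions, and the plan does not let the reader choose between them. Nor does it say why pain on a 0–10 scale should follow a logistic distribution. If the parent is normal, the margin at 24 per group shrinks to about one point (0.912 or 0.909 against 0.90). Simulations of scores rounded and clipped to 0–10, with assumed group means of 3 v 1, 4 v 2 and 5 v 3 and SD 2, give 0.896 to 0.909 under a normal parent and 0.928 to 0.932 under a logistic one. On this view, one sentence naming the method would settle the matter at almost no cost.

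Part of this stands. The calculation option is missing, and a mislabelled parent is possible. But it is not proven, because the stated label reproduces the stated number. The bounded-scale runs use raw scores with assumed means, whereas the primary outcome is a change in pain, which can be negative; they are only a rough guide, and their worst case is 0.4 points below 0.90. Rewriting the sentence around a normal parent and the A.R.E. method would credit the sponsor with a calculation that no document shows was run.

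**Conclusion.** The concern does not hold as an arithmetic error. With d = 1, a two-sided 0.05 test and a logistic parent, 24 per group gives 0.905 by the formula that reproduces the plan, 0.933 by simulation and up to 0.945 by the A.R.E. method. The stated 90% is therefore met, and is conservative by about 3 points if simulation is taken as the truth. Reading the plan the other way would at most say that 21 or 22 per group suffice, which is 2 or 3 fewer than planned and no reason to recruit fewer.

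What remains is an unstated calculation option in an otherwise full specification. Whichever answer the sponsor gave, 24 evaluable and 30 enrolled per group would stay, and no test, error rate or conclusion would move. This rests on the plan's difference of 2 and SD of 2 and on treating the outcome as continuous. With a normal parent the simulated power is still 0.909, although Noether's cruder approximation gives 0.878.
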